4.7.3 Endpoints

4.7.3.1 Primary Endpoint

The primary endpoint of this study is fever (Days 1 through 8), defined as oral temperature $\geq 101^{\circ}$ F. Comparison of the rate of fever between the 2 treatment groups will be based on the upper limit of the two-sided 95% exact CIs for the rate increase (bivalent vaccine minus placebo) evaluated against the pre-specified equivalence criterion of 5 percentage points.

This corresponds to the null hypothesis of:

H0: Rate difference \geq 5 percentage points.

The alternative hypothesis is:

HA: Rate difference < 5 percentage points.

A two-sided 95% CI will be constructed using the exact method based on the score statistic proposed by (Chan and Zhang, 1999). This method computes the lower and upper confidence limits by inverting 2 separate one-sided tests of half the nominal Type I error rate. Its test statistic is based on the score statistic that is computed as the observed difference of the 2 binomial event rates minus the hypothesized value of the rate difference (observed rate difference) divided by the standard error of this difference under the alternative hypothesis. This test assures that the Type I error does not exceed the pre-specified level. Due to discreteness when the sample size is relatively small compared to the expected event rate, the associated Type I error rate could be quite conservative, that is, smaller than the pre-specified level.

4.7.3.2 Secondary Endpoints

Secondary endpoints of the study include other reported solicited symptoms and AEs that occur within 7 days after vaccination (Days 1-8), and all solicited symptoms and AEs that occur within 14 days after vaccination (Days 1-15). Additional secondary endpoints include SAEs and NOCDs that occur within 28 days after vaccination (Days 1-29) and within 180 days after vaccination (Days 1 through 181).

Fever will be summarized according to the following thresholds:

- Oral $> 100^{\circ}$ F
- Oral $\geq 101^{\circ}$ F
- Oral $> 102^{\circ}F$
- Oral $> 103^{\circ}F$

A secondary analysis comparing rates of other solicited symptoms (Days 1-8) between the 2 treatment groups will be performed. Exact two-sided 95% CIs (Chan and Zhang, 1999) on the rate difference (bivalent vaccine minus placebo) will be constructed. There are no prespecified equivalence criteria for the secondary analyses.

The number of days of solicited symptoms and the proportion of subjects experiencing each event by study day will be presented without formal statistical comparison. The distribution of the number of days with each individual event will also be summarized without formal statistical comparison. The proportion of subjects using antipyretic and analgesic agents within 7 days after vaccination (Days 1-8) and 14 days after vaccination (Days 1-15) will be summarized by treatment group.

4.7.4 Interim Analysis

A safety analysis will be conducted after all subjects have been followed through Day 15 and all data through at least Day 8 are locked. The analysis for Days 1 through 15 will include the primary endpoint of this study (fever for Days 1-8, defined as oral temperature $\geq 101^{\circ}$ F), as well as analysis of safety data (solicited symptoms and AEs), and antipyretics and analgesic use reported within 7 days and within 14 days after dosing. To ensure the blinding of each subject's treatment assignment throughout the study, the Day 15 unblinded analyses will be performed by defined MedImmune personnel (see Section 4.5.3.2). Subsequently the unblinded results will be reviewed by the project statistician, medical monitor, therapeutic area vice president, and the Head of Clinical Biostatistics and Data Management prior to approving the release of the unblinded study results to the project team. Since the results of the interim analysis for the primary endpoint will be final, the treatment codes will be sent to Patient Safety within 1 business day of the release of the study results to update the safety databases. Study site personnel and contract research organization personnel directly associated with the conduct of this study and the subjects will remain blinded to the treatment assignment for individual subjects until the completion of the study.

The results of the interim analysis will be reported to regulatory authorities in order to receive authorization for release of the commercial product including the tested new vaccine virus strains.

After the study is complete and the database is locked, all data through 180 days after dosing will be summarized by treatment group using the safety population.

5 ASSESSMENT OF SAFETY

5.1 Definition of Adverse Events

The ICH Guideline for Good Clinical Practice E6(R1) defines an AE as:

Any untoward medical occurrence in a patient or clinical investigation subject administered a pharmaceutical product and which does not necessarily have a causal relationship with this treatment. An AE can therefore be any unfavorable and unintended sign (including an abnormal laboratory finding), symptom, or disease temporally associated with the use of a medicinal product, whether or not considered related to the medicinal product.

An AE includes but is not limited to any clinically significant worsening of a subject's preexisting condition. An abnormal laboratory finding (including electrocardiogram finding) that requires medical intervention by the investigator, or a finding judged by the investigator as medically significant should be reported as an AE. If clinical sequelae are associated with a laboratory abnormality, the diagnosis or medical condition should be reported (eg, renal failure, hematuria) not the laboratory abnormality (eg, elevated creatinine, urine red blood cell increased). Abnormal laboratory values that are not, in the investigator's opinion, medically significant and do not require intervention should not be reported as AEs.

Adverse events may be treatment emergent (ie, occurring after initial receipt of investigational product) or nontreatment emergent. A nontreatment-emergent AE is any new sign or symptom, disease, or other untoward medical event that begins after written informed consent has been obtained but before the subject has received investigational product.

Elective treatment or surgery or preplanned treatment or surgery (that was scheduled prior to the subject being enrolled into the study) for a documented pre-existing condition that did not worsen from baseline is not considered an AE (serious or nonserious). An untoward medical event occurring during the prescheduled elective procedure or routinely scheduled treatment should be recorded as an AE or SAE.

5.2 Definition of Serious Adverse Events

An SAE is any AE that:

- Results in death
- Is immediately life-threatening
- Requires inpatient hospitalization or prolongation of existing hospitalization
- Results in persistent or significant disability/incapacity
- Is a congenital anomaly/birth defect in offspring of the subject
- Is an important medical event that may jeopardize the subject or may require medical intervention to prevent one of the outcomes listed above

Medical or scientific judgment should be exercised in deciding whether expedited reporting is appropriate in this situation. Examples of medically important events are intensive treatment in an emergency room or at home for allergic bronchospasm, blood dyscrasias, or convulsions that do not result in hospitalizations; or development of drug dependency or drug abuse.

5.3 Definition of Solicited Symptoms

Solicited symptoms are events that are considered likely to occur post dosing. For this study, solicited symptoms include:

- Fever (> 100°F [37.8°C] oral)
- Runny nose
- Sore throat
- Cough

- Vomiting
- Muscle aches
- Chills
- Decreased activity (tiredness)
- Headache

5.4 Definition of New Onset Chronic Diseases

An NOCD is a newly diagnosed medical condition that is of a chronic, ongoing nature and is assessed by the investigator as medically significant. Examples of NOCDs include but are not limited to diabetes, asthma, autoimmune disease (eg, lupus, rheumatoid arthritis), and neurological disease (eg, epilepsy, autism). Events that would not be considered NOCDs are mild eczema, diagnosis of a congenital anomaly present at study entry, or acute illness (eg, otitis media, bronchitis). An NOCD should also be reported as an SAE if it meets the definition in Section 5.2. If an NOCD occurs within 14 days post dosing, the event should also be reported as an AE (Section 5.1).

5.5 Recording of Adverse Events

Adverse events will be recorded on the eCRF using a recognized medical term or diagnosis that accurately reflects the event. Adverse events will be assessed by the investigator for severity, relationship to the investigational product, possible etiologies, and whether the event meets criteria of an SAE and therefore requires immediate notification to MedImmune Patient Safety. See Section 5.2 for the definition of SAEs and Appendix 2 for guidelines for assessment of severity and relationship. If an AE evolves into a condition that meets the regulatory definition of "serious," it will be reported on the SAE Report Form.

5.5.1 Time Period for Collection of Adverse Events

Adverse events will be collected from time of signature of informed consent throughout the treatment period and including the follow-up period through 14 days post dosing (Days 1 through 15).

All SAEs will be recorded from the time of informed consent through 180 days post dosing (Days 1 through 181).

5.5.2 Recording of Solicited Symptoms

Solicited symptoms will be reported using the terms as defined in this protocol (Section 5.3). Oral thermometers and safety assessment worksheets will be distributed to subjects on the day of investigational product administration. Beginning on the evening of the day of investigational product administration through 14 days after receipt of investigational product (Days 1 through 15), the subject will record on the worksheets his/her temperature and the
occurrence of solicited symptoms. Temperatures should be taken at approximately the same time each day (preferably in the evening); however, if multiple temperatures are taken during a given day, the highest temperature should be recorded on the worksheet regardless of the time of day taken.

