4.6.2 Prohibited Concomitant Medications

Other than the medications described above, use of concomitant medications including overthe-counter medications, herbal supplements, vitamins, etc, from Day 1-15 is discouraged. Subjects must be instructed not to take any medications, including over-the-counter products, without first consulting with the investigator.

Use of antipyretic or analgesic medications for all symptoms other than temperatures $\geq 101^{\circ}$ F oral (or equivalent) is discouraged from Day 1-15. All medications taken during the 14-day post vaccination follow-up period, the indications, the start and stop dates of the medications, and the route of administration will be recorded from the time of informed consent through Day 15.

The following medications are exclusionary. The sponsor must be notified if a subject receives any of these during the study.

- 1 Any vaccine or investigational agent from 30 days prior to randomization through 30 days post investigational product administration
- 2 Any intranasal medication from 14 days prior to through 14 days post investigational product administration
- 3 Receipt of influenza antiviral therapy or antiviral agents within 48 hours prior to investigational product administration or expected receipt of influenza antiviral therapy or antiviral agents through 14 days after receipt of investigational product

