4.7.2 Sample Size and Power Calculations

It is expected that almost all subjects will provide information on safety and tolerability. Table 4 summarizes the solicited event rates following FluMist and placebo vaccination in healthy adults 18 through 64 years of age in Study AV009.

Number of Subjects	FluMist ^a	Placebo ^a	Difference in Proportions	95% CI ^b
Randomized	3,041	1,520		
Who returned diary cards	2,985	1,490		
Who experienced solicited events	n (%)	n (%)		
Fever				
Oral temperature > 100.0°F	40 (1.34)	20 (1.34)	-0.00	(-0.01, 0.01)
Oral temperature $\geq 101.0^{\circ}$ F	17 (0.57)	9 (0.60)	-0.00	(-0.01, 0.00)

Table 4Summary of Solicited Events (Days 0 Through 7) in Study AV009

Number of Subjects	FluMist ^a	Placebo ^a	Difference in Proportions	95% CI ^b
Oral temperature > 102.0°F	2 (0.07)	2 (0.13)	-0.00	(-0.01, 0.00)
Oral temperature > 103.0°F	0	0	0.00	(-0.00, 0.00)
Runny nose	1,323 (44.32)	397 (26.64)	0.18	(0.15, 0.21)
Sore throat	793 (26.57)	243 (16.31)	0.10	(0.08, 0.13)
Cough	407 (13.64)	152 (10.20)	0.03	(0.01, 0.06)
Headache	1,172 (39.26)	555 (37.25)	0.02	(-0.01, 0.05)
Muscle aches	481 (16.11)	216 (14.50)	0.02	(-0.00, 0.04)
Chills	247 (8.28)	91 (6.11)	0.02	(0.00, 0.04)
Tired/weak	733 (24.56)	306 (20.54)	0.04	(0.01, 0.07)
Any solicited event	2,117 (70.92)	919 (61.68)	0.09	(0.06, 0.12)

Table 4	Summary of Solicited Events	(Days 0 Through 7) in Study AV009
			,

CI = confidence interval

^a Subjects counted if they experienced an event at least once within 7 days following vaccination.

^b Confidence intervals for the difference in proportions are based on an exact method.

Power to show a similar fever rate with 300 evaluable subjects (240 bivalent vaccine and 60 placebo recipients) for varying true fever rates ranging from 0.5% to 2.0% in placebo recipients is presented in Table 5. Accordingly, the currently proposed study will provide at least 98% power to rule out a rate increase of 5 percentage points assuming the true difference between the treatment groups is zero and the true fever rate is $\leq 1\%$. Power is lower if the true difference is different from zero. For example, if the true fever rates are 2% and 1% in vaccine and placebo recipients, respectively, the power will be 77%.

True Fever Rate			
Vaccine	Placebo	Exact Power ^a	Exact Type I Error Rate
0.5%	0.5%	99.9%	2.2%
1.0%	1.0%	98.0%	2.3%
1.5%	1.5%	92.6%	2.3%
2.0%	2.0%	85.0%	2.3%
2.0%	1.0%	77.0%	2.3%
3.0%	1.0%	43.9%	2.3%

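### No temperature reading is prompted before an antipyretic or analgesic dose, so a fever masked by a dose taken for another symptom can go unrecorded, in the direction that favours passing

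*Combined protocol and SAP*

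**What the plan says.** Section 4.7.3.1 sets the endpoint: "The primary endpoint of this study is fever (Days 1 through 8), defined as oral temperature" of at least 101°F. The comparison uses the "upper limit of the two-sided 95% exact CIs for the rate increase", judged against a "pre-specified equivalence criterion of 5 percentage points".

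Section 5.5.2 gives the diary rule: "Temperatures should be taken at approximately the same time each day (preferably in the evening"). The same sentence adds that when several readings are taken in a day, the highest is entered whatever its time. The section asks for no clock time and ties no reading to a medication dose.

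On medication, Section 4.6.2 states that "Use of antipyretic or analgesic medications for all symptoms other than temperatures" of 101°F or more is discouraged on Days 1-15. Subjects are also told to consult the investigator before taking anything. The items to be recorded are indication, start and stop dates, and route; times are not listed. Section 4.6.1 names analgesics among permitted supportive care. Exclusion criterion 13 removes people expected to use these drugs daily or every other day. Section 4.2.3.2 provides calls every day or every other day to Day 15.

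On analysis, Section 4.7.3.2 offers one item: "The proportion of subjects using antipyretic and analgesic agents within 7 days after vaccination" (and within 14 days), summarised by treatment group. Section 4.7.3.1 has no rule for readings taken after a dose.

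**The concern.** The test succeeds by showing little excess fever. A subject with a true temperature of 101°F or more can take an analgesic for headache in the afternoon, measure in the evening, and be entered as afebrile. That removes an event. If the same share of events is lost in both arms, the difference shrinks by that share; if more are lost in the vaccine arm, it shrinks further. Either way the upper limit moves away from the 5-point margin.

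Section 3.2.3 treats fever as the marker of insufficient attenuation. Section 4.7.4 makes the Day 15 result for this endpoint final and sends it to regulators to support product release. The statement in Section 4.7.3.1 that Type I error is held covers recorded fever. It does not cover true fever if some events are systematically missed.

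The loss cannot be repaired at analysis. With medication dates but no times, and a daily highest temperature with no time, the listed data cannot show whether a normal reading came before or after a dose on the same day.

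**Working it through.** **Inputs from the documents.** "300 evaluable subjects (240 bivalent vaccine and 60 placebo recipients") from Section 4.7.2. The margin is 5 points. The interval comes from "inverting 2 separate one-sided tests of half the nominal Type I error rate" (Section 4.7.3.1), so the relevant test is one-sided at 0.025.

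**Assumed input.** m is the share of truly febrile subjects for whom no reading of 101°F or more is recorded on Days 1-8. The documents give no value. Figures below use m from 0 to 30%.

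**Test.** With x_V and x_P the fever counts,

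Z = (x_V/240 − x_P/60 − 0.05) / √[p̃_V(1−p̃_V)/240 + p̃_P(1−p̃_P)/60],

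where p̃_V = p̃_P + 0.05 are the maximum-likelihood rates constrained to the margin. The p-value is the largest value, over all placebo rates, of the probability of a Z at or below the observed one. The trial passes if p ≤ 0.025. This gives the following pass region:

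| Placebo fevers | Most vaccine fevers that still pass |
|---|---|
| 0 | 5 |
| 1 | 7 |
| 2 | 9 |
| 3 | 11 |

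**Reproducing Table 5.** Summing the two binomial distributions over the pass region:

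| True rates, vaccine / placebo | Stated power | Recomputed |
|---|---|---|
| 0.5% / 0.5% | 99.9% | 99.89% |
| 1.0% / 1.0% | 98.0% | 97.98% |
| 1.5% / 1.5% | 92.6% | 92.61% |
| 2.0% / 2.0% | 85.0% | 85.02% |
| 2.0% / 1.0% | 77.0% | 76.99% |
| 3.0% / 1.0% | 43.9% | 43.88% |

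Type I error at a placebo rate of 1% is 2.33%, against 2.3% stated. The plan's calculation stands.

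**Effect of masking.** With equal masking, the observed rates are p_V(1−m) and p_P(1−m), so the observed difference is (p_V − p_P)(1−m). On the margin, true 6% versus 1%:

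| m | Observed rates | Observed difference | Pass probability |
|---|---|---|---|
| 0 | 6.0% / 1.0% | 5.0 points | 2.3% |
| 10% | 5.4% / 0.9% | 4.5 points | 4.2% |
| 20% | 4.8% / 0.8% | 4.0 points | 7.4% |
| 30% | 4.2% / 0.7% | 3.5 points | 12.9% |

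The pass probability reaches 5% at m of about 13%. If only vaccine recipients are masked, it is 4.7% at m = 10% and 8.9% at m = 20%.

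**Away from the margin.**
- True 8% versus 1%: 0.18% with no masking, 0.44% at m = 10%, 1.07% at m = 20%.
- True 11% versus 1%: below 0.2% for m up to 30%.
- True 1% in both arms: 97.98% with no masking, 99.15% at m = 20%.

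**The case against.** The plan has several real safeguards, and a reader might infer more than the documents support.

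*That only one evening reading counts.* It does not. Evening is a preference, one reading is what is prompted, and the highest of several is entered. This helps only when an extra reading is taken, and nothing links one to a dose.

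*That nothing protects the fever endpoint.* This is wrong. Use is discouraged, the investigator is consulted first, regular users are excluded, and calls are frequent. The 101°F exception in Section 4.6.2 also presupposes a reading when the drug is taken for fever, and that reading would be entered as the day's highest. The gap left is narrow: a dose for another symptom, in someone who is also febrile, before that day's only reading. A fever with a reading of 101°F or more on any other day of the window is still counted.

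*That Study AV009 shows masking is common.* Its headache rates (39.26% and 37.25%) and muscle-ache rates (16.11% and 14.50%) count any occurrence in 7 days. They are not rates of analgesic use, still less of use on a febrile day. The package insert gives 28% headache over 14 days for FluMist Quadrivalent in adults 18 through 49, which is this trial's age range.

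*That the false-pass rate is known to be inflated.* No masked share is documented, and the table on the margin is the most sensitive case. Calling a pass there false also presumes that the 5 points refer to all true fevers and not to fevers measured under this schedule.

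These arguments limit the size of the problem. They do not supply the missing prompt, and neither consulting the investigator nor a telephone call recovers an unmeasured temperature.

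**Conclusion.** The point holds as a limited measurement gap. The plan can be followed exactly and still lose fevers, the loss favours passing, and the listed data would not reveal it. If 10% to 20% of fevers were masked equally in both arms, a true excess exactly at the margin would pass 4.2% to 7.4% of the time instead of 2.3%. The masked share is an assumption throughout. The effect is small once the true excess is well above 5 points, and it barely matters when the arms are truly equal. The documents do not support a claim about how often masking will occur, nor any criticism of the power calculation, which reproduces. The change is worth making because it is cheap and must be in place before subjects are dosed.

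**What to change.** In Section 5.5.2 and on the safety assessment worksheet, instruct subjects to take and record a temperature immediately before any antipyretic or analgesic dose on Days 1-15, and whenever they feel feverish. Keep the highest-reading rule. The instruction changes nothing about when medication may be taken. Separately, Sections 4.6.1 and 4.6.2 describe analgesics in different terms and should be reconciled.

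Add a worksheet flag for any day with such a dose and no pre-dose reading. Report the number of flagged subjects by arm beside the primary result, as a descriptive check. Flagged subjects should not be counted as fevers. That would push the trial toward failure by construction: if equal rates of 5% in both arms counted as fever, the exact pass probability would be 46%, and at 10% it would be 25%.

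The cost is one instruction, one flag and one line in a table. The downsides are slightly more burden for subjects, slightly more fevers detected in both arms, and slightly less comparability with earlier studies if those relied on a once-daily reading.

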5.5.3 Follow-up of Unresolved Adverse Events

Any AEs that are unresolved at the subject's last AE assessment in the study are followed up by the investigator for as long as medically indicated. MedImmune retains the right to request additional information for any subject with ongoing AE(s)/SAE(s) at the end of the study, if judged necessary.

5.6 **Reporting of Serious Adverse Events**

All SAEs have to be reported, whether or not considered causally related to the investigational product, or to the study procedure(s). All SAEs will be recorded in the eCRF.

If any SAE occurs in the course of the study, then Investigators or other site personnel inform the appropriate Sponsor representative(s) within 1 day ie, immediately but no later than 24 hours of when he or she becomes aware of it.

The designated Sponsor study representative works with the Investigator to ensure that all the necessary information is provided to the Sponsor Patient Safety data entry site within 1 calendar day of initial receipt for fatal and life threatening events and within 5 calendar days of initial receipt for all other SAEs.

For fatal or life-threatening adverse events where important or relevant information is missing, active follow-up is undertaken immediately. Investigators or other site personnel must inform Sponsor study representatives of any follow-up information on a previously reported SAE within 1 calendar day ie, immediately but no later than 24 hours of when he or she becomes aware of it.

Once the Investigators or other site personnel indicate an AE is serious in the Electronic Data Capture (EDC) system, an automated email alert is sent to inform the designated Sponsor study representative(s).

If the EDC system is not available, then the Investigator or other study site personnel reports a SAE to the appropriate Sponsor study representative by telephone. The Sponsor study representative will advise the Investigator/study site personnel how to proceed.

